16.2.2. QUALITATIVE SUBJECT STATUS ASSESSMENTS

16.2.2.1. Qualitative Subject Status Variables & Derivations

The following parameters will be used to assess the qualitative status of subjects:

- Summary and change from baseline in global impression assessments by the Investigator and parent(s)/caregiver(s)
 - Clinical Global Impression of Severity (CGI-S)
 - Clinical Global Impression of Improvement (CGI-I)
- Change from baseline in scores for:
 - Impact of Pediatric Epilepsy Scale (IPES)

For subjects who previously completed INS011-14-029, the IPES that are completed on Visit 2 (Day 1) of INS011-14-030 will serve as the baseline. Analysis will also be done using the Visit 2 (Day 1) data in INS011-14-030 as the baseline.

The schedule of assessments is provided in [Table 1](#) of the protocol. Subjects enrolled from INS011-15-054 will be excluded from IPES scores evaluation.

For CGI-S, the assessment for each subject by time point will be recorded on a scale of 1 to 7:

- 1 = Normal
- 2 = Borderline
- 3 = Mild
- 4 = Moderate
- 5 = Marked
- 6 = Severe
- 7 = Most extreme.

The CGI-I assessment for each subject will also be a scale of 1 to 7:

- 1 = Very much improved
- 2 = Much improved
- 3 = Minimally improved
- 4 = No change
- 5 = Minimally worse
- 6 = Much worse
- 7 = Very much worse.

Document: C:\Users\q832483\Documents\Insy CSR\Pending\Ready for QC\New folder\Statistical Analysis Plan.docx
Author: [REDACTED] Version Number: V1.0 Final
Version Date: 04APR2017

Template No: CS_TP_BS016 – Revision 3
Effective Date: 01May2012

Reference: CS_WI_BS005

STATISTICAL ANALYSIS PLAN: PROTOCOL INS011-14-030

Page 25 of 40

The IPES is validated for subjects who are 2 to 16 years of age. Due to developmental delay characteristic of the study population, subjects through 18 years of chronological age will complete the IPES.

The IPES is an 11-item questionnaire in which parents rate the degree to which their child's epilepsy has affected major aspects of their family and child's health-related quality of life. This includes the impact on their child's overall health, relationships, social life, academics, self-esteem, family activities, and the parents' own hopes for their child's future. Each item is scored on a four point scale:

- 0 = Not at all (epilepsy does not affect the area in question)
- 1 = A little
- 2 = Some
- 3 = A lot (epilepsy greatly affects functioning in the given area)

All of the items are then added to produce an IPES total score. The IPES also includes a numeric scale of the child's overall quality of life ranging from 1 = "Poor" to 6 = "Excellent".

16.2.2.2. Missing Data Methods for Qualitative Subject Status Variable(s)

All data will be evaluated as observed; no imputation method for missing values will be used. A subject who withdraws prior to the last planned observation in a trial period will be included in the analyses up to the time of withdrawal (for any reason). Missing data will result in a reduced sample size for that variable/parameter.

16.2.2.3. Analysis of Qualitative Subject Status Variables

The qualitative subject status will be summarized as follows:

- Number of subjects (and corresponding percentage) along the 7-point scale by time point and age category separately for CGI-S and CGI-I completed by the parent(s)/caregiver(s) and the Investigator
- Shift from baseline in CGI-S score over time separately as regards if it's completed by the parent(s)/caregiver(s) or the Investigator
- Descriptive statistics (n, mean, SD, median, minimum, and maximum) over time and by age category of the actual numeric score and the change from baseline for CGI-S completed by the parent(s)/caregiver(s) and the Investigator
- Descriptive statistics (n, mean, SD, median, minimum, and maximum) over time and by age category of the actual numeric score for CGI-I completed by the parent(s)/caregiver(s) and the Investigator
- Descriptive statistics (n, mean, SD, median, minimum, and maximum) over time and by age category of actual scores and the change from baseline for the different items of IPES

For each change/shift from baseline analysis, the two baselines, as defined [Section 6.2](#), will be used in separate tables.

Each of the above items will also be summarized by CBD status for results observed at the Follow-up visit.

Results for each assessment will be listed separately to support these tables.

Document: C:\Users\q832483\Documents\Insy CSR\Pending\Ready for QC\New folder\Statistical Analysis Plan.docx
Author: [REDACTED] Version Number: V1.0 Final
Version Date: 04APR2017

Template No: CS_TP_BS016 – Revision 3
Effective Date: 01May2012

Reference: CS_WI_BS005

17. SAFETY OUTCOMES

All outputs for safety outcomes will be based on the SAF.

There will be no statistical comparisons between the treatment groups for safety data.

17.1. ADVERSE EVENTS

Adverse Events (AEs) will be coded using the latest version of MedDRA central coding dictionary.

Treatment emergent adverse events (TEAEs) are defined as AEs that first occur or worsen in severity after the first administration of the study medication.

See [Appendix 1](#) for handling of partial dates for AEs. In the case where it is not possible to define an AE as treatment emergent or not, the AE will be classified by the worst case; i.e. treatment emergent.

An overall summary of number of subjects within each of the categories described in the sub-section below, will be provided as specified in the templates. In the summaries, AEs will be counted only once per subject. Only those AEs that begin between start and end of study will be summarized.

Each summary described in Adverse Event section (except [Section 17.1.2](#) and [Section 17.1.3](#)) will be repeated for TEAEs observed during the Follow-up period and presented by CBD status.

Listings will include TEAEs and Non-TEAEs.

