5.1 Screening Period (Visit 1)

Subjects that do not rollover within 14 days of completing their previous study (INS011-14-029) will be required to complete a Screening Visit. Subjects who enroll after participating in INS011-15-054 will not need to complete a Screening Visit if less than 14 days has elapsed between dosing.

The following procedures will be completed only after obtaining informed consent:

- Review of inclusion and exclusion criteria (see Sections 3.4.1 and 3.4.2)
- Record concomitant medications and concomitant procedures
- Obtain a 12-lead ECG
- Record vital signs (blood pressure, heart rate, respiratory rate, and temperature measurements)
- Draw blood samples for hematology and chemistry (fasting NOT required) and record whether subject was fasting at time of collection in the eCRF
- Obtain a urine sample for urinalysis
- Obtain a blood sample for serum pregnancy test in female subjects of childbearing potential
- Perform a complete physical examination (see Section 6.1.5.2), including height and weight

- Perform a neurological examination (see Section 6.1.5.2), including assessment for developmental capabilities
- Record demographic data
- Record medical and surgical history
- Record recent medication history including current AEDs, vitamins, herbal preparations, blood products, and over-the-counter drugs
- Record AEs and SAEs
- Administer Investigator CGI-S
- Administer parent(s)/caregiver(s) CGI-S
 - When appropriate, subjects will complete the CGI-S for themselves.
- Administer C-SSRS (if appropriate).

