5.2.1 Visit 2 (Day 1)

Since Day 11 for INS011-14-029 may represent the first visit of this study, activities that have been carried out in the previous protocol will not be repeated and the data will be used in the analysis of both studies provided the assessments are completed within 14 days prior to administration of the first dose of Cannabidiol Oral Solution in INS011-14-030 (to avoid repetition of procedures). Similarly, all assessments completed during the Screening Period (Visit 1), and within 14 days prior to administration of the first dose of Cannabidiol Oral Solution in INS011-14-030, may be used for the Visit 2 (Day 1), except vital signs.

If not already completed in the past 14 days, the following procedures will be completed PRIOR to administration of the morning dose of the investigational product:

- Obtain informed consent
 - The ICF must be completed prior to any procedures.
- Review of inclusion and exclusion criteria (see Sections 3.4.1 and 3.4.2).
- Record concomitant medications and concomitant procedures.
- Obtain a 12-lead ECG.
- Record vital signs (blood pressure, heart rate, respiratory rate, and temperature measurements). Vital signs must be assessed regardless of date of last collection.
- Draw blood samples for hematology and chemistry (fasting NOT required) and record whether subject was fasting at time of collection in the eCRF.
- Obtain a urine sample for urinalysis.
- Obtain a urine sample for β human chorionic gonadotropin (β -hCG) pregnancy test in female subjects of childbearing potential.
- Complete blood draw for plasma levels.
- Perform a complete physical examination (see Section 6.1.5.2), including height and weight.
- Perform a brief neurology examination (see Section 6.1.5.2).
- Administer morning dose of the investigational product in the clinic.
- Record demographic data.
- Record medical and surgical history.

- Record and review current AEDs
- Dispense investigational product
- Review of dosing procedures for the investigational product
- Record AEs and SAEs
- Administer Investigator CGI-S
- Administer parent(s)/caregiver(s) CGI-S
 - When appropriate, subjects will complete the CGI-S for themselves.
- Administer IPES
 - The IPES is validated for subjects who are 2 to 16 years of (developmental) age. Due to developmental delay characteristic of the study population, subjects through 18 years of chronological age will complete the IPES.
- Administer VABS

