8.3.4.1 AEs

The TEAEs are defined as AEs that first occur or worsen in severity after the first administration of the investigational product. Such AEs will be coded using the MedDRA coding dictionary and will be summarized by presenting the number and percentage of subjects having any AE, having an AE in each SOC, and having each individual AE as reported by PT. Furthermore, a summary for SAEs and summaries by severity and relationship to the investigational product will be presented by dose and overall. The most frequent (5%) AEs and drug related AEs will also be provided.

All percentages will be based on the number of subjects in the Safety Population.

In the summaries, AEs will be counted only once per subject. If a subject reports the same AE more than once, it will be counted with its worst severity and closest relationship to investigational product. Only those AEs that begin between start and end of study will be summarized.

The AEs will also be listed by subject and dose.

Subject death due to any cause and subjects with AEs leading to investigational product discontinuation will be listed and summarized by dose and overall.

The proportion of subjects that discontinue investigational product or experience dose interruption due to treatment emergent AEs will be summarized by dose and for all subjects.

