APPENDIX 1. PARTIAL DATE CONVENTIONS

Imputed dates will NOT be presented in the listings.

ALGORITHM FOR TREATMENT EMERGENCE OF ADVERSE EVENTS:

START DATE	STOP DATE	ACTION
Known	Known	If start date < study med start date, then not TEAE If start date >= study med start date, then TEAE
	Partial	If start date < study med start date, then not TEAE If start date >= study med start date, then TEAE
	Missing	If start date < study med start date, then not TEAE If start date >= study med start date, then TEAE
Partial, but known components show that it cannot be on or after study med start date	Known	Not TEAE
	Partial	Not TEAE
	Missing	Not TEAE
Partial, could be on or after study med start date	Known	If stop date < study med start date, then not TEAE If stop date >= study med start date, then TEAE
	Partial	Impute stop date as latest possible date (i.e. last day of month if day unknown or 31st December if day and month are unknown), then: If stop date < study med start date, then not TEAE If stop date >= study med start date, then TEAE
	Missing	Assumed TEAE
Missing	Known	If stop date < study med start date, then not TEAE If stop date >= study med start date, then TEAE

Document: C:\Users\q832483\Documents\Insy CSR\Pending\Ready for QC\New folder\Statistical Analysis Plan.docx
Author: [REDACTED] Version Number: V1.0 Final
Version Date: 04APR2017

Template No: CS_TP_BS016 – Revision 3
Effective Date: 01May2012

Reference: CS_WI_BS005

STATISTICAL ANALYSIS PLAN: PROTOCOL INS011-14-030

Page 37 of 40

START DATE	STOP DATE	ACTION
	Partial	Impute stop date as latest possible date (i.e. last day of month if day unknown or 31st December if day and month are unknown), then: If stop date < study med start date, then not TEAE If stop date >= study med start date, then TEAE
	Missing	Assumed TEAE

ALGORITHM FOR PRIOR / CONCOMITANT MEDICATIONS:

START DATE	STOP DATE	ACTION
Known	Known	If stop date < study med start date, assign as prior If stop date >= study med start date and start date <= end of treatment, assign as concomitant If stop date >= study med start date and start date > end of treatment, assign as post study

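### The TEAE definition includes AEs that worsen after first dose, but SAP Appendix 1 has no branch for worsening, so a pre-dose AE that worsens on the same record is left out of the TEAE tables

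*SAP*

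**What the plan says.** **Definition.** SAP 17.1 defines TEAEs as "AEs that first occur or worsen in severity after the first administration of the study medication". Protocol 8.3.4.1 has the same two limbs: "AEs that first occur or worsen in severity after the first administration of the investigational product".

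**Summary restriction.** SAP 17.1 adds "Only those AEs that begin between start and end of study will be summarized". Protocol 8.3.4.1 contains the same sentence. Neither document defines the start of the study.

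**Algorithm.** SAP Appendix 1 is titled as a set of partial-date conventions, but it contains an algorithm for treatment emergence that includes rows with fully known dates. For a known start date the rule is "If start date < study med start date, then not TEAE". A partial start date that must be earlier than first dose gives the same result. A start on the first-dose date or later gives a TEAE.

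**Fallback.** Under SAP 17.1, an AE whose treatment emergence cannot be determined is classed as treatment-emergent.

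**Records and listings.** At the Screening Visit the site is to "Record AEs and SAEs" (Protocol 5.1). AE recording is also on the Visit 2 list, under the instruction that "the following procedures will be completed PRIOR to administration of the morning dose of the investigational product" (Protocol 5.2.1). Protocol 6.1.2 asks for a separate entry for each event but does not say whether a rise in severity counts as one. SAP 17.1 states: "Listings will include TEAEs and Non-TEAEs".

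**The concern.** The definition has two limbs and the rules that carry it out serve only one. A programmer who follows Appendix 1 will class an AE that began before the first extension dose as not treatment-emergent, even if it goes from mild to severe during the extension.

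This matters more here than in a first-exposure study. Subjects roll over from studies of the same product, preferably without interruption, so some may enter with an AE already under way. The Protocol Synopsis makes the incidence and severity of TEAEs and SAEs the primary criterion. No hypothesis tests are planned, so the descriptive AE tables are the main result. Where the gap operates, it works in one direction only, towards lower incidence or lower severity. The SAP's other defaults run the opposite way: missing severity becomes severe, and undeterminable emergence becomes TEAE.

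Tables could also disagree. A subject who stops because of such a worsening could be counted under the adverse-event reason in disposition (SAP 9) and in dose modification (SAP 14), yet be absent from the table of TEAEs leading to discontinuation (SAP 17.1.3).

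**Working it through.** The plan gives no figure to reproduce. The check is whether the definition and Appendix 1 classify the same AE in the same way.

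**Inputs.** The definition is from SAP 17.1 and Protocol 8.3.4.1. The algorithm is from SAP Appendix 1: four kinds of start date by three kinds of stop date, 12 rows, none using severity or a date of worsening. The first dose is taken as the first extension dose, which is how SAP 6.1 and the intra-study baseline in SAP 6.2 read together.

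**Rules as formulas.**
- Definition: TEAE if onset is on or after first dose, or if worsening is on or after first dose. (First-dose-day onsets are counted, to match Appendix 1.)
- Appendix 1: a known start gives TEAE only if start ≥ first dose. A partial start certainly before first dose gives not TEAE. For any other partial or missing start, TEAE if stop ≥ first dose (a partial stop is set to its latest possible date) or if stop is missing.

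**Test cases** (days relative to first extension dose; in cases a to e the AE worsens after that dose)

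| Case | Definition | Appendix 1 |
|---|---|---|
| a. Ongoing from previous study, known start 8 days before, worsens 30 days after | TEAE | not TEAE |
| b. Onset in screening, 3 days before, worsens 5 days after | TEAE | not TEAE |
| c. Partial start, certainly before | TEAE | not TEAE |
| d. Partial start that could be on or after, stop known and after | TEAE | TEAE |
| e. Start and stop both missing | TEAE | TEAE |
| f. New AE 10 days after | TEAE | TEAE |

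The rules conflict in cases a, b and c: start date known, or certain, to be before first dose, with later worsening. The fallback does not rescue these cases, because Appendix 1 returns a definite answer.

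**The sentence about when an AE begins.** Its limits are the start and end of the study, not the first dose. It excludes case a by itself, because that onset precedes this study. It need not exclude case b: if the study starts at consent or screening, the AE passes this sentence and only Appendix 1 removes it.

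**Size per missed subject** (formula: 100/N)
- N = 80, the maximum in Protocol 3.4: 100/80 = 1.25 points.
- N = 60, if only subjects from INS011-14-029 enrol: 100/60 = 1.67 points.
- SAP 17.1.1 reports by age category, but category sizes are not given. Assuming 10, 20 or 30 subjects: 10.0, 5.0 or 3.3 points.
- The list of frequent TEAEs uses a 5% cut-off. At N = 80 that is 0.05 × 80 = 4 subjects. With one of four missed, 3/80 = 3.75% and the term leaves the list.

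A preferred-term row falls only if the subject has no other TEAE with that term. The any-TEAE row falls only if the subject has no other TEAE at all. The number of affected subjects cannot be computed from the documents.

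**The case against.** **Appendix 1 may not be meant to override the definition.** SAP 17.1 refers to it for partial dates, and its title says the same, so a programmer could apply the definition directly. That is a possible reading, but the appendix labels its table as the treatment-emergence algorithm and includes known-date rows. Two instructions that give different answers on the primary criterion should not be left to the programmer.

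**The eCRF may already solve it.** If sites open a new record at worsening, the new start date makes it a TEAE. The request for separate entries per event and the rule for an AE reported more than once (worst severity taken) are both compatible with that. This stands as a limit on the point, but neither document requires the practice.

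**Few pre-dose records may exist.** This also stands. Screening is needed only when the rollover gap exceeds 14 days. Visit 2 may coincide with Day 11 of INS011-14-029. An onset on the first-dose day is already a TEAE. AEs ongoing at rollover might be held as current medical history (SAP 11). A reader might take the statement in Protocol 5.2.1 that "the data will be used in the analysis of both studies" as proof that earlier AE records are carried over, but its context is avoiding repeat procedures. The planned listing of non-TEAEs does not prove that any will occur. Such records may exist; the documents do not show that they will.

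**Other outputs remain.** Listings keep the event. The disposition and dose-modification summaries and the death summary in SAP 17.2 do not use the TEAE flag. Laboratory and vital-sign changes are also compared with the previous-study baseline. The damage is therefore bounded, but the TEAE tables still carry the primary criterion.

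**Conclusion.** The contradiction is real, and the plan is wrong as written rather than merely short of detail. An AE that meets the definition by worsening is classed as not treatment-emergent by Appendix 1 whenever its start date is known, or certain, to precede the first extension dose. It then drops out of the TEAE summaries by SOC, preferred term and severity (SAP 17.1.1), and out of the tables for interruption (SAP 17.1.2), discontinuation (SAP 17.1.3) and serious TEAEs (SAP 17.1.4).

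The effect rests on two conditions that the documents leave open: the AE is held on an AE record with onset before the day of the first extension dose, and the worsening stays on that record. It also assumes that Appendix 1 is applied as written.

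Two stronger readings should be resisted. A reader might infer that the sentence on when AEs begin excludes every worsened earlier AE by itself. It does so only for onsets before the undefined start of this study; for onsets between consent and first dose, Appendix 1 alone excludes. A reader might also infer that the reported TEAE rates will be materially understated. The documents support a per-subject size only, not a count. The point should be fixed before database lock, mainly because the repair is cheap.

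**What to change.** 1. In SAP 17.1, change the restriction so that it covers AEs that begin *or worsen in severity* during the study, and define the start of the study. Record the departure from the matching sentence of Protocol 8.3.4.1 in SAP 3.3. Protocol 8.2.1 allows this before database lock without a protocol amendment.

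2. Make worsening operative by one of two routes, according to how the eCRF holds severity:
   - **A. Severity is held with dates within a record.** Add an Appendix 1 branch: start before the first extension dose and higher severity on or after that dose gives a TEAE, dated at the worsening and carrying the higher severity.
   - **B. One severity per record.** Require a new AE record with its own start date at each worsening, including worsening of a condition held as medical history. Appendix 1 then classes it as a TEAE without a new branch.

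3. State whether AEs ongoing at rollover are held as AE records or as medical history.

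**Cost.** SAP wording and minor programming under route A. Route B needs an eCRF completion instruction and possibly site queries for worsenings already entered on an old record. TEAE counts may become slightly less favourable.

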17.1.1. ALL TEAEs

TEAEs will be summarized by presenting the number and percentage of subjects having any TEAE, having any TEAE in each SOC, and having each individual TEAE as reported by PT. Furthermore, summaries by severity and relationship to the study medication will be presented according to the definition below. The most frequent (at least 5%) TEAEs and drug related TEAEs will also be provided.

For each summary, TEAEs will be reported by age category.

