Endpoints	
• Incidence, type, and severity of AEs and SAEs associated with Cannabidiol Oral Solution as an adjunctive treatment for seizures• Changes from baseline in the previous study in vital signs• Changes from baseline in the previous study in ECG findings if appropriate• Changes from baseline in the previous study laboratory values (hematology, chemistry, and

urinalysis)

- Trough (steady state) concentrations of Cannabidiol Oral Solution throughout approximately 48 weeks of continuous exposure, inclusive of the subject's treatment on their previous study

Efficacy-related Data to be Reported

- Frequency, duration, and severity of seizures (i.e., seizure control).
- Parent(s)/caregiver(s) CGI-I and CGI-S.
- Investigator CGI-I and CGI-SIPES, C-SSRS, and VABS scores, Subjects enrolled from INS011-15-054 will be excluded from IPES, VABS, and C-SSRS scores evaluation.

Criteria for evaluation: A record of the incidence and severity of treatment-emergent AEs (TEAEs) and SAEs throughout the study is the primary criterion. Other safety-related parameters such as 12-lead ECG and hematology, chemistry, and urinary analyses will also be assessed.

Plasma levels of cannabidiol and its 7-hydroxy (OH) metabolite will be evaluated (trough levels). For subjects taking clobazam, levels of clobazam and its major metabolite (norclobazam) will be measured if there are safety concerns.

Secondary outcome measures will include control of seizures (frequency, duration, and severity of seizures compared to baseline in the previous study), overall changes in global impression assessments by the Investigator and parent(s)/caregiver(s) (CGI-I and CGI-S), and change from baseline in IPES, VABS, and C-SSRS scores, Subjects enrolled from INS011-15-054 will be excluded from IPES, VABS, and C-SSRS scores evaluation.

Statistical methods: The sample size will be determined by the number of subjects that are eligible and elect to rollover from INS011-14-029 and INS011-15-054 into this study.

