duration of treatment in INS011-14-030 will be based on the length of time they were enrolled in INS011-15-054 such that total duration of treatment in both studies combined will not exceed approximately 48 weeks. Subjects visit entry into INS011-14-030 will be determined at the discretion of the sponsor and the investigator.

The study will be terminated upon 1 of the following:

- The investigational product is successfully approved for marketing in the US
- Sponsor elects to terminate INS011-14-030.

Treatment with established background AEDs will continue without interruption and changes will be permitted as necessary based on safety concerns or due to changes in seizure control as described in Section 4.3.

As described in Table 1 and Section 5.0, visits will be scheduled at Week 1, Week 2, then monthly for 3 months, and then quarterly thereafter. A Screening Visit will be required for all subjects that do not rollover within 14 days of completing their previous study. All subjects will complete the Final Visit/ Discontinuation Visit regardless of when they stop treatment/complete the study. A Follow-up Visit will occur 2 weeks after the Final Visit/Discontinuation Visit.

At each visit, a record of the incidence and severity of adverse events (AEs), treatment-emergent AEs (TEAEs), and SAEs will be collected and this will serve as a primary outcome criterion for this study. Other safety-related parameters such as 12-lead ECG and hematology, chemistry, and urinary analyses will also be assessed at specified visits. Determination of trough plasma levels of cannabidiol and its 7-OH metabolite will be performed at each visit except Visits 3 and 4 (Week 1 and Week 2). This will support safety monitoring and establish the extent of variability during long-term treatment with the investigational product. For subjects taking clobazam, levels of clobazam and its major metabolite (norclobazam) will be measured if there are safety concerns. Seizure diaries will be reviewed to assess control of seizures (frequency, duration, and severity) throughout the duration of the study.

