8.2.2 General

Since this is an extension study of INS011-14-029 and INS011-15-054 data for INS011-14-030 will be presented for the extension period only (i.e., not for the entire period spanning INS011-14-029 and INS011-15-054 and INS011-14-030 studies).

Categorical variables will be summarized using frequencies and percentages. Continuous variables will be summarized using descriptive statistics (number, mean, standard deviation [SD], median, minimum, and maximum).

Baseline for this study will be the same as that defined in protocols INS011-14-029 and INS011-15-054, respectively. Additionally, all data from this study will also be compared to the intra-study baseline (data from the subject's first visit [i.e., Visit 1 [Screening] or Visit 2 [Day 1]]). For assessments that were not completed in INS011-14-029 (i.e., IPES and VABS), the only baseline will be data collected at Visit 2 (Day 1) of INS011-14-030. (Data from subjects enrolling through INS011-15-054 may be excluded from the analysis)

Data collected at unscheduled time points will not be summarized at the unscheduled time points.

Data will be presented for each dose (10, 20, and 40 mg/kg/day) and for all doses combined together (overall), corresponding to the dose at which subject will initiate this study (as described in Section 4.1). When appropriate, raw data will be presented by visit (Visit 1

[Screening], Visit 2 [Day 1], Visit 3 [Week 1], Visit 4 [Week 2], then monthly for 3 months, and then quarterly thereafter).

No statistical hypothesis testing is planned for this study.

A detailed SAP will be finalized prior to database lock.

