Subjects will receive twice daily oral doses of Cannabidiol Oral Solution for approximately 48 weeks or until the IP is successfully approved for marketing in the US (whichever occurs earlier), inclusive of their treatment on the previous study. For subjects that completed INS011-14-029, 48 weeks of treatment would be completed under this protocol. For subjects that participated in INS011-15-054, duration of treatment in INS011-14-030 will be based on the length of time they were enrolled in INS011-15-054 such that total duration of treatment in both studies combined will not exceed approximately 48 weeks. Subjects visit entry into INS011-14-030 will be determined at the discretion of the sponsor and the investigator. All subjects will complete the Final Visit/Discontinuation Visit regardless of when they stop treatment/complete the study. A Follow-up Visit will occur 2 weeks after the Final Visit/Discontinuation Visit.

If the subject is not going to continue to receive IP offered under the Investigator IND Expanded Access Program, the subject may be tapered off Cannabidiol Oral Solution based on the investigator's preference and subject's tolerability. The investigator should ensure that the taper is planned well in advance to allow sufficient time to complete the taper prior to the Visit 10 at 48 weeks (± 10 days). The date of entering the Expanded Access Program will be documented in the electronic case report form (eCRF).

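### TEAE and SAE incidence is planned only as crude percentages, although time on the extension differs by design with the source study

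*SAP*

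**What the plan says.** The protocol synopsis, under criteria for evaluation, sets the outcome: "A record of the incidence and severity of treatment-emergent AEs (TEAEs) and SAEs throughout the study is the primary criterion".

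- **Summary measure.** SAP 17.1.1 plans "presenting the number and percentage of subjects having any TEAE", with breakdowns by system organ class, preferred term, severity and relationship, and a table of events reaching 5%, all by age category. SAP 17.1.4 adds a summary of serious TEAEs by class and term. The synopsis (statistical methods) describes TEAE and SAE summaries alike as numbers and percentages.
- **Denominator.** Protocol 8.3.4.1: "All percentages will be based on the number of subjects in the Safety Population".
- **Window.** SAP 17.1: "Only those AEs that begin between start and end of study will be summarized". Protocol 8.2.2 says data "will be presented for the extension period only".
- **Planned exposure.** SAP 3.1: "For subjects that completed INS011-14-029, 48 weeks of treatment would be completed under this protocol". For the other source, Protocol 3.1 says "duration of treatment in INS011-14-030 will be based on the length of time they were enrolled in INS011-15-054", and SAP 3.1 adds "such that total duration of treatment in both studies combined will not exceed approximately 48 weeks". Protocol 8.1 caps the two sources at 60 and 20 subjects.
- **Exposure tables.** SAP 14 tabulates days of exposure and subjects dosed per time point, by age category and overall.

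Protocol 3.1 and SAP 3.1 also describe the 48 weeks as including treatment in the previous study. That does not sit with a full 48 weeks here for INS011-14-029 subjects, and the passages should be reconciled. The point below does not depend on how.

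**The concern.** Someone observed for 12 weeks has less opportunity to report a first event than someone observed for 48, yet both count as one in the denominator. Because parent-study events and time are left out, nothing makes up the difference for INS011-15-054 subjects. Withdrawal, sponsor termination or marketing approval (Protocol 3.1 and 3.4.3) can shorten exposure further for anyone.

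Two uses of the tables are at stake. The overall percentage in a long-term safety study is readily taken as the risk over the planned 48 weeks. And the age columns will be read across, even though source study, which drives planned exposure, is not a display factor in the SAP. The 5% cut-off for the most frequent events is applied to the same crude percentages.

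**Working it through.** **Inputs from the documents.** 60 subjects from INS011-14-029 and 20 from INS011-15-054; 60 + 20 = 80, which reproduces the stated maximum. Extension treatment is 48 weeks for the first group.

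**Inputs assumed.** The documents give neither event rates nor time spent in INS011-15-054. I take a 48-week risk p of 10%, 30% or 60%, t = 12, 24 or 36 extension weeks for all 20 INS011-15-054 subjects, a constant hazard and no dropout.

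**Formulas.**
- Hazard: λ = −ln(1 − p)/48.
- Expected crude risk over t weeks: q = 1 − exp(−λt) = 1 − (1 − p)^(t/48).
- Pooled crude percentage: (60p + 20q)/80.
- Shortfall: p minus the pooled figure, which equals 0.25 × (p − q).

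Example, p = 30% and t = 24: q = 1 − 0.7^0.5 = 16.3%; pooled = (18 + 3.27)/80 = 26.6%; shortfall 3.4 points.

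| p | t (weeks) | q | Pooled | Shortfall (points) |
|---|---|---|---|---|
| 10% | 12 | 2.6% | 8.1% | 1.9 |
| 10% | 24 | 5.1% | 8.8% | 1.2 |
| 10% | 36 | 7.6% | 9.4% | 0.6 |
| 30% | 12 | 8.5% | 24.6% | 5.4 |
| 30% | 24 | 16.3% | 26.6% | 3.4 |
| 30% | 36 | 23.5% | 28.4% | 1.6 |
| 60% | 12 | 20.5% | 50.1% | 9.9 |
| 60% | 24 | 36.8% | 54.2% | 5.8 |
| 60% | 36 | 49.7% | 57.4% | 2.6 |

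**Age categories.** If a share f of a category comes from INS011-15-054, its expected percentage is (1 − f)p + fq. At p = 30% and t = 24 this is 30.0% for f = 0, 26.6% for f = 0.25, 23.2% for f = 0.5 and 16.3% for f = 1. If f is the same in every category, the artefact between them is zero.

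**The 5% table.** A term with a 48-week risk of 5.5% has q = 1 − 0.945^0.5 = 2.79% at t = 24. The expected pooled figure is (60 × 0.055 + 20 × 0.0279)/80 = 3.86/80 = 4.8%, below the cut-off.

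**What a rate would show.** At p = 30% the first-event rate is 100 × 52 × 0.3567/48 = 38.6 per 100 subject-years (52-week years) in both source groups, whatever t is. That equality follows from the constant hazard.

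**Sensitivity to that assumption.** Put half of the 48-week cumulative hazard in the first 8 weeks, with p = 30%. If the risk clock restarts at extension Day 1, the pooled figure is 27.0%, 28.0% or 29.0% at t = 12, 24 or 36. If the early risk of INS011-15-054 subjects already fell in the parent study, it is 23.8%, 25.0% or 26.2%. A rate would then depend on follow-up too.

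**The case against.** The strongest reply is that nothing in the plan is miscalculated. No section defines the percentage as a 48-week risk, and the proportion of subjects with an event over actual follow-up is a legitimate description in a single-arm study with no hypothesis tests (Protocol 8.2.2, SAP 6.5). That stands. A reader might infer that incidence is simply understated; the documents support this only against a 48-week risk, which is a target the plan does not name.

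A reader might also infer that the displayed groups are not comparable. The documents do not show it. Displays are by age category, the age mix of INS011-15-054 subjects is not given, SAP 17 plans no safety comparison, and the follow-up displays by CBD status share a nominal 2-week period. The problem arises only if INS011-15-054 subjects cluster in some age categories.

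SAP 14 is a genuine mitigation: a reader can see unequal exposure by age category. But it corrects no TEAE percentage and does not separate the source studies.

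Finally, SAP 8 and 17.1 leave table content to templates that I have not seen. The statement that no rates are planned therefore rests on the SAP text.

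**Conclusion.** The gap is real and moderate. The primary safety outcome is specified only as crude n (%) of the Safety Population, while planned extension time differs between the two source studies and events outside the extension are not counted. At most a quarter of subjects (20 of 80) have shorter exposure by design. Over the assumed grid the pooled figure falls 0.6 to 9.9 points below the 48-week risk; the large values need both a common event and little extension time left. The true size cannot be determined from the documents.

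Distortion between age categories is a possibility that depends on the source mix. This is a worthwhile, cheap reporting improvement and does not make the planned percentages wrong.

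**What to change.** Keep n (%) in SAP 17.1.1 and 17.1.4, and add to the TEAE and SAE tables, overall and by age category:

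- subject-years at risk, and subjects with a first event per 100 subject-years;
- a cumulative-incidence or onset-interval display, because the rate is easy to interpret only under a roughly constant hazard;
- any-TEAE and SAE results by source study.

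Define time at risk as first extension dose to first event or, without an event, to the end of AE observation. The SAP 14.1 duration should not be used unmodified: it is last dose minus first dose plus 1, it is not cut at the first event, and it ends at the last dose, whereas Protocol 6.1.1 records AEs through the Follow-up Visit. Keep the 5% table as planned, with the rate beside the percentage.

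Onset and dosing dates are already collected, so the cost is SAP wording, extra table columns and a few displays. The downside is the constant-hazard assumption behind the rates.
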